6.0 Administration of Pharmacologic Agent

Armodafinil or placebo will begin after enrollment and will continue daily for a total of 4 weeks.

Patients will pick up the assigned study medication at one of the outpatient pharmacy stations in MD Anderson. At pickup, patients will receive instruction on how to take study medications (Appendix EEE). If the patient is unable to pick up the study medication, the investigational pharmacy will mail the study medication to the patient home, overnight.

The participants will take study medication enterally, once daily, in the morning, starting after study entry and continuing for 28 days (4 weeks). The dosing schedule for the symptom intervention agent is described in the table below.

Study medication use will be reviewed at the end of week 4 by study staff. Patients will be asked to bring their study medication to the clinic if they are coming in for a routine visit, at which time study staff will perform a medication count. If the patient is not coming to the clinic at study completion, the medication review will be completed by telephone. Results of the count will be recorded on the Study Medication Accountability form (Appendix K).

During the end of week 4 assessment, the study staff will also offer the participant the option to receive open label armodafinil, at the same dosing schedule described in the table below. If the patient agrees to the optional open label extension, they will either pick-up armodafinil during their routinely scheduled follow-up visit or the pharmacy will mail it to them. A 5-day window will be allowed between the end of Part I and the start of the optional open label extension.

Symptom Intervention Agent	Dosage Forms	Total daily dose: starting day 1 of week 1
Armodafinil or matching placebo	50mg and 100mg capsules or tablets	50 mg the first 3 days, 100 mg the next 4 days, and 150 mg for the remaining treatment period.*

*capsules or tablets, one every morning, may be given without regard to meals. This dosing schedule is to be followed during the 4-week symptom intervention and the optional open label extension.

Patients who are satisfied with the study medication and express interest in continuing will be able to consult with their physicians about the risks and benefits of continuing the armodafinil; if they elect to continue, further clinical monitoring will be provided by the patient's treating physician. Patients with persistent moderate to severe levels of fatigue will be offered further evaluation. MD Anderson patients will be referred at the MD Anderson Fatigue Clinic. Patient's final disposition will be collected on the Patient Disposition Form (Appendix V).

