4.1 Absolute Contraindications, Cautions, and Warnings about Armodafinil

4.11 Absolute Contraindications

4.111 Pre-existing psychosis or bipolar disorder

4.112 Pre-existing renal impairment; Severe chronic renal failure (CrCl < or = 20 mL/min) increased modafinil acid 9 fold

4.113 Pre-existing cirrhosis or hepatic impairment

4.114 Pre-existing Tourette's syndrome

4.115 Patient should not be breastfeeding, pregnant, or planning to become pregnant while on armodafinil

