8.0 Patient Eligibility

8.1 Inclusion Criteria

8.11 Patients who were treated with either definitive or postoperative radiation or chemoradiation therapy for HNC with moderate to severe levels of patient reported fatigue, at 6 or more weeks after completing all planned cancer therapy.

Patients who rated their fatigue level at 5 or greater on a 0 to 10 scale during any follow-up clinic visits at MD Anderson.

8.12 Male and female patients \geq 18 years old.

8.13 Patients who speak English (due to the novel research and its complexity, we are only accruing English-speaking patients to the protocol).

8.14 Patients must agree to discontinue any current herbal supplement use, and refrain from taking any herbal supplement while on protocol.

8.15 Patients must be willing and able to review and understand informed consent documents and to provide written consent.

8.16 Women of childbearing potential (women who are not postmenopausal for at least 1 year and are not surgically sterile) must have a negative urine pregnancy test.

8.17 Sexually active males and females must agree to use effective birth control or to be abstinent for the duration of the study period.

8.18 Women currently taking birth control pills or planning to start birth control pills must agree to an additional method of birth control (either abstinence or a barrier method) while on the study medication and for 1 additional month after study completion.

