9.0 Patient Enrollment and Registration

Patient Enrollment

Patients will be screened for eligibility and recruited for enrollment in the outpatient Head and Neck Cancer Clinic in the Department of Radiation Oncology at MD Anderson, 6 or more weeks after completing planned cancer therapy (this time line will generally coincide with the first follow up appointment for most patients with HNC treated with radiation therapy). By this time, most patients should have had significant improvement in their radiation therapy-related mucositis, dermatitis, and pain. Recruitment brochures will be available to give to the patients in the clinic (Appendices ZZ and ZZZ).

Patients with major depressive disorder or severe depression (a score of 13 or greater on the BDI Fast Screen (BDI-FS) will be excluded. If this is the case, we will notify their treating physician for appropriate management or referral. The first disease/treatment response assessment is made around this time period as well.

Women of child-bearing potential who want to participate will be told that we will perform a mandatory pregnancy screening test through a urine sample at baseline. Study staff will provide the pregnancy kits to these women and make sure the results are known and recorded in the follow-up notes in Clinic Station before study drug prescription are filled by the Investigational Pharmacy. If the pregnancy test is positive the patient will be excluded from the study.

Research staff will maintain a log of all patients screened, and the reasons that patients do not enter the study will be documented.

Eligible patients who agree to enroll in the study will provide written informed consent/authorization.

At enrollment, patients will be informed that they will receive a \$40 stipend for participating in the pilot study. The stipend will be distributed in \$20 increments twice during the study, at enrollment and at study completion.

Enrolled patients will be registered into the Clinical Oncology Research System (CORe), the MD Anderson institutional patient data management system.

Patient Randomization and Assignment to Treatment Arm

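### In the supplied protocol body, open-label armodafinil can be released at week 4 without a new pregnancy test, so a placebo-arm woman's first exposure could rest on a baseline test at least 28 to 33 days old

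*Combined protocol and SAP*

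**What the plan says.** The design (Section 5.0) gives 4 weeks of blinded armodafinil or placebo, then an optional 4 weeks of open-label armodafinil.

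Section 6.0 governs the second supply: "During the end of week 4 assessment, the study staff will also offer the participant the option to receive open label armodafinil". A patient who agrees either collects the drug at a routine visit "or the pharmacy will mail it to them". On timing, "A 5-day window will be allowed between the end of Part I and the start of the optional open label extension". The week 4 medication review may be done by telephone if no visit is due. The section names no pregnancy test before release.

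Section 4.115 lists pregnancy among the absolute contraindications: "Patient should not be breastfeeding, pregnant, or planning to become pregnant while on armodafinil".

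Section 9.0 sets the control for the first supply. Women of childbearing potential are told that "we will perform a mandatory pregnancy screening test through a urine sample at baseline", and staff must "make sure the results are known and recorded in the follow-up notes in Clinic Station before study drug prescription are filled". Criterion 8.16 requires that test to be negative.

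Other rules bear on the same risk. Under 8.17, "Sexually active males and females must agree to use effective birth control or to be abstinent for the duration of the study period". Under 8.18, women on the pill "must agree to an additional method of birth control", and 8.222 excludes those unwilling to do so. Criterion 8.221 excludes women planning pregnancy, and 12.15 takes a patient off study if she becomes pregnant.

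**The concern.** For Part I the protocol does not rely on contraception commitments alone. It adds a test and makes the recorded result a condition of filling the prescription. The extension is a second prescription for the same drug. For every placebo patient who opts in, it is also the first exposure to the active drug. In the supplied text, that second release follows the patient's agreement and has no matching hold.

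What is at stake is fetal exposure to a drug that the protocol itself treats as absolutely contraindicated in pregnancy. A pregnancy that began during the 4 blinded weeks, and that the woman does not yet know about, would not be caught by any step stated in the body before the drug was mailed.

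**Working it through.** The plan gives no figure on this point, so the check is a day count and a comparison of the two releases.

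**Inputs.** Part I is 28 daily doses (Section 6.0). The gap before open-label drug is 0 to 5 days (Section 6.0). The extension is 4 weeks, taken here as 28 daily doses (Section 5.0). I assume the baseline test is done on day 1; if it is done earlier, every test age below rises by the same number of days.

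**Day count.**
- Part I doses: days 1 to 28. Test age at the last Part I dose: 28 − 1 = 27 days.
- First open-label dose with no gap: 28 + 1 = day 29. Test age: 29 − 1 = 28 days.
- First open-label dose after the full window: 28 + 5 + 1 = day 34. Test age: 34 − 1 = 33 days.
- Last open-label dose: 29 + 27 = day 56 to 34 + 27 = day 61. Test age: 55 to 60 days.

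So the whole open-label exposure of a placebo-arm woman can rest on one test that is already 28 to 33 days old at her first dose.

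**The two releases side by side.**

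| | Part I supply | Open-label supply |
|---|---|---|
| Trigger | Enrollment and randomization | Patient agreement at week 4 |
| Pregnancy test stated | Urine test at baseline | None stated in the body |
| Prescription held for a result | Yes (9.0) | Not stated (6.0) |
| Age of test at first dose | 0 days if done on day 1 | 28 to 33 days |

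**Could Section 9.0 already cover the second supply?** Its hold could be read as applying to any study drug prescription. The result it refers to is still the baseline one, so on that reading the hold is met by the old result.

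**Do the other rules detect a pregnancy?** Criteria 8.17, 8.18, 8.221 and 8.222 make one less likely. Criterion 12.15 acts once a pregnancy is known, and no test is tied to it. Weekly telephone monitoring (11.1) can pick up a pregnancy that the woman reports, but not one she is unaware of.

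**How many women?** The documents do not give the number of women of childbearing potential or the expected uptake of the extension. The only ceiling is the planned placebo arm of 20, so I claim no count.

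**The case against.** The strongest objection is that absence cannot be shown. Section 10.0 sends the reader to Appendix X for the full assessment schedule, which is where a repeat test would normally be listed, and that appendix was not supplied. This stands. The point is limited to the protocol body, and a cross-reference would settle it if the test is already scheduled.

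A second objection is that this is a choice of test interval. Part I itself allows 28 days of armodafinil on one test, and the contraception duties run for the whole study period, which under Section 5.0 includes the extension. This carries some weight and keeps the point small. It does not remove it: in Part I the first exposure follows a result recorded for that prescription, and at week 4 the first exposure of a placebo patient need not.

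A reader might infer more than this, in two ways that the documents do not support.

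- *That open-label drug is released under no conditions at all.* The Section 12 removal criteria apply throughout. A patient who meets one of them (pregnancy, severe rash or hypersensitivity, liver tests, INR, psychosis, cardiovascular events) is off study and not a candidate for the extension. What is missing from the body is a check tied to week 4.
- *That a rash below grade 3 of uncertain cause is left without a rule.* Sections 4.70 and 5.0 tell patients to stop the drug as soon as a body rash appears, whatever its grade or cause, and Section 5.0 brings in the PI. Criterion 12.14 removes for hypersensitivity with no grade limit. What is unwritten is a rule on restarting, or on entering the extension, after such a stop; PI management would sensibly fill that gap. It is also rare. At the 1% rate quoted in 4.31 for 150 mg, 20 × 0.01 = 0.2 rashes of any grade are expected on armodafinil. At under 1% on placebo, fewer than 0.2 more are expected, so fewer than 0.4 among 40 patients. Those rates come from other populations, and only some such rashes would be low grade, of uncertain cause and followed by acceptance of open-label drug.

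**Conclusion.** The point holds as a cheap improvement to patient safety. In the supplied body, the only stated pregnancy test is at baseline, and release of open-label armodafinil is not tied to a new one. A placebo-arm woman of childbearing potential could have her first exposure on day 29 to 34, on a test at least 28 to 33 days old. The existing contraception and removal rules reduce the risk without detecting a pregnancy. The number of women affected is unknown and likely small in a 40-patient trial.

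This rests on three assumptions: the baseline test is done on or before day 1, the open-label course starts within the stated window, and Appendix X does not already require a repeat test. Confidence is medium because of the last. The rash question is an optional clarification and not a separate error.

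**What to change.** Add one sentence to Section 6.0: women of childbearing potential in both arms repeat the urine pregnancy test at the end of Part I, and a negative result is recorded before the open-label prescription is filled or mailed. Testing both arms avoids any need to unblind. If Appendix X already requires this, cross-reference it in Section 6.0.

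The cost is one urine kit for each such woman who opts in. When the drug is mailed, the kit must be mailed too and the result reported by telephone, which may use part of the 5-day window. Rarely, a patient will not enter the extension. That leaves the 4-week AUC of Section 5.0 untouched. Section 13.21, however, builds the primary variable from 8 weeks of BFI scores, so under that text a withheld extension could affect her later scores.

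Optionally, the same paragraph could say that a patient who stopped study drug for rash is offered open-label drug only after the PI documents a non-drug cause. This costs one PI note per rash, and a few patients whose rash was unrelated may miss the extension.

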The safety and effectiveness of NUVIGIL in individuals older than 65 years have not been systematically evaluated. One open-label study showed decreased clearance and an increased half-life in volunteers over the age of 65 years. A lower dose of NUVIGIL should be considered in elderly patients because elimination of NUVIGIL and its metabolites may be reduced as a consequence of aging (Darwish et al, 2010).

To our knowledge, there are no published cancer-related studies with armodafinil. Studies of modafinil, however, have shown its beneficial action on cancer symptoms. A randomized, placebo-controlled, double-blind phase III trial showed modafinil was effective in improving fatigue in cancer patients receiving chemotherapy, although only for patients with severe baseline fatigue scores (Jean-Pierre et al, 2010). A pilot study of 30 patients with brain tumors receiving therapy showed reductions in fatigue severity scores at 8 weeks (ES 1.14) and at 12 weeks (ES 1.21) (Kaleita et al., 2006). In studies of noncancer diseases, the effect size of modafinil in reducing fatigue has been reported to be between 0.57 (multiple sclerosis, Zifko et al., 2002) and 2.00 (biliary cirrhosis, Jones & Newton, 2007). Studies have reported its beneficial effect on mood and cognition (MacDonald et al., 2002; Taneja et al., 2007). Compared with placebo, modafinil improved cognitive performance in breast cancer survivors who had shown a favorable response to modafinil in the preceding open-label phase of the same study (Kohli et al., 2007). Modafinil has been used to augment treatment with selective serotonin reuptake inhibitors (SSRIs) or bupropion in patients with major depression accompanied by residual fatigue and sleepiness (DeBattista et al., 2003; Konuk et al., 2006). Modafinil has also been used to combat opioid-induced sedation in patients with chronic pain (Webster et al., 2003).

Armodafinil is commercially available as 50mg, 150mg, and 250mg tablets. We will purchase commercial grade drug and matching placebo to be dispensed by the investigational pharmacy.

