7.5 Work Productivity and Activity Impairment Questionnaire (WPAI) (Appendix H)

7.6 Head and Neck Treatment Summary Form (Appendix O)

7.7 Patient Contact Form (Appendix P)

7.8 Demographic Form The Demographic Form includes patient birth date, gender, marital status, race, ethnicity, education, and employment status (Appendix Q). The Demographic Form will be completed at baseline.

7.9 Charlson Comorbidity Index The Charlson Comorbidity Index yields a comorbidity score, to control for serious concurrent chronic disease conditions (Charlson et al., 1994) (Appendix R).

7.10 On-Study Form The On-Study Form contains data about disease, previous treatment, whether a patient is on concurrent protocols (Appendix S). This form will be completed at baseline.

7.11 Clinical Monitoring Form The Clinical Monitoring Form contains clinical data, including Body Mass Index (BMI), blood pressure, pulse rate, performance status, symptom treatment, and CTC toxicity scores (Appendix T).

7.12 Medication Form The Medication Form contains data about types of medications patients have been prescribed. Medication types include pain medications, antiemetics, and psychotropics among others. There is also a general section for other types of medications patients may be taking. (See Appendix U).

7.13 Patient Disposition Form Patient's final disposition will be collected on the Patient Disposition Form. Patients who are satisfied with the study medication and express interest in continuing will be able to discuss continuing armodafinil as part of physician-patient decision based on a risk-benefit scenario, with further clinical monitoring to continue under the care of the patient's treating physician. Subjects with persistent moderate to severe levels of fatigue will be offered further evaluation and referral to the MD Anderson Fatigue Clinic (Appendix V).

7.14 Study Medication Accountability Form This form contains study medication data, including the number of tablets dispensed to the patient at the last visit to the outpatient pharmacy, how many tablets were returned from the last visit, and the number of days the tablets were taken (Appendix K).

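### Section 6.0 contradicts itself on units per day: no single 50 mg or 100 mg unit supplies the 150 mg daily dose set for 21 of 28 days, and 100 mg is not among the commercial strengths in Section 4.0

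*Combined protocol and SAP*

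**What the plan says.** The dosing table in Section 6.0 makes three statements about armodafinil or matching placebo.

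- Dosage forms: "50mg and 100mg capsules or tablets".
- Total daily dose: "50 mg the first 3 days, 100 mg the next 4 days, and 150 mg for the remaining treatment period".
- Footnote on how it is taken: "capsules or tablets, one every morning, may be given without regard to meals".

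The text above the table sets a single morning administration for 28 days. The footnote also carries the table into the extension: "This dosing schedule is to be followed during the 4-week symptom intervention and the optional open label extension".

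On supply, Section 4.0 states: "Armodafinil is commercially available as 50mg, 150mg, and 250mg tablets". It continues: "We will purchase commercial grade drug and matching placebo to be dispensed by the investigational pharmacy". Section 5.0 repeats the purchase statement. The supplied text does not describe over-encapsulation or compounding, and does not give the number of units for each dose step.

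Section 7.14 describes the accountability form. It records tablets dispensed, tablets returned and "the number of days the tablets were taken".

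**The concern.** The grammatical subject of the footnote is the capsule or tablet, so its natural reading is one unit each morning. On that reading the footnote, the forms and the dose column are incompatible from day 8 onward. Section 4.0 does not settle the matter, because its list of strengths differs from the table's.

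Three things depend on the answer.

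- **Exposure.** The daily dose is the intervention under test, and Section 13.1 says the trial is meant to supply effect size estimates for a larger study. Patients take the drug at home and may receive it by mail. Section 6.0 places the review of medication use at the end of week 4, possibly by telephone. The weekly calls in Section 11.1 are described as adverse event monitoring. A misreading could therefore run for much of Part I. Section 13.23 keeps non-compliant patients in the analysis, so any shortfall would tend to dilute the estimated effect.
- **Accountability.** A tablet count can be read as adherence only if the units per day are known.
- **Placebo matching.** Placebo has to match active drug in strength and in units at every step.

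**Working it through.** **Inputs.** From Section 6.0: forms of 50 and 100 mg; 50 mg for 3 days, 100 mg for 4 days, then 150 mg; a 28-day course; one unit each morning, reading the footnote literally. From Section 4.0: commercial tablets of 50, 150 and 250 mg.

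**Step 1: days at 150 mg.** 28 − 3 − 4 = 21 days, and 21/28 = 75% of Part I.

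**Step 2: which steps can be met, and with how many units.** These combinations test consistency only; none is a recommendation.

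| Daily dose | Fewest units from 50/100 mg (Section 6.0) | Fewest units from 50/150/250 mg (Section 4.0) |
|---|---|---|
| 50 mg | 1 | 1 |
| 100 mg | 1 | 2 (50 + 50) |
| 150 mg | 2 (50 + 100) | 1 |

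With the Section 6.0 forms, one unit a day fails at the 150 mg step. With the Section 4.0 strengths, it fails at the 100 mg step. Neither list supports one unit each morning across all three steps.

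**Step 3: exposure over 28 days.**

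- Scheduled: 3 × 50 + 4 × 100 + 21 × 150 = 150 + 400 + 3,150 = 3,700 mg.
- At most one 50 or 100 mg unit a day: 3 × 50 + 4 × 100 + 21 × 100 = 150 + 400 + 2,100 = 2,650 mg.
- Shortfall: 3,700 − 2,650 = 1,050 mg, and 1,050/3,700 = 28%. On days 8 to 28 it is 50/150 = 33% a day.

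**Step 4: units a fully adherent patient would use in 28 days.**

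- One unit daily: 28.
- Fewest 50/100 mg units: 3 × 1 + 4 × 1 + 21 × 2 = 49.
- 50 mg units only: 3 × 1 + 4 × 2 + 21 × 3 = 74.
- Fewest Section 4.0 tablets: 3 × 1 + 4 × 2 + 21 × 1 = 32.

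Full adherence could therefore correspond to anything from 28 to 74 units, depending on a rule that the protocol body does not state consistently.

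**The case against.** The strongest reply is that the dose itself is not in doubt. The column is headed as a total daily dose and gives each step in milligrams. The listed forms reach every step once more than one unit is allowed. Only the word for a single unit stands in the way, and it may loosely mean one dose, echoing the once-daily instruction in the body text. A pharmacy dispenses the drug, with instruction at pickup, and is likely to work from the milligram column. This stands, and it limits the consequence: the documents do not show that anyone would be dispensed at most 100 mg a day.

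A second reply is that Section 4.0 describes commercial tablets as background, while Section 6.0 speaks of capsules or tablets. Capsules may point to pharmacy-prepared units, which would explain a 100 mg form. That is possible, so the absence of 100 mg from the commercial list does not show that the form is unobtainable. However, the supplied text does not mention such preparation and twice says commercial grade drug will be purchased.

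Third, the patient instructions (Appendix EEE) and the accountability form (Appendix K) are not in the supplied text and may give the units for each step. The description in Section 7.14 is compatible with any fixed number of units, so it is not itself in conflict. This also stands. Even if the appendices are clear, the protocol body would still need correcting.

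A reader might infer that the 150 mg dose cannot be given, that the armodafinil arm will receive 28% too little, or that a null result would be uninterpretable. The documents do not support these readings. Each needs the footnote to be taken literally and to override an explicit milligram schedule for three weeks.

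**Conclusion.** The contradiction is real, and the table is wrong as written rather than merely short of detail. Taking the footnote to mean one unit, the Section 6.0 forms cannot supply the dose set for 21 of 28 days. The Section 4.0 strengths cannot supply the 100 mg step on days 4 to 7. The mismatch between the two lists of strengths remains even if the footnote means one dose.

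The size is conditional. The 28% shortfall is the smallest that a literal one-unit reading allows with the table's forms over a 28-day course; it is not a forecast. The same wording governs the open-label extension. No endpoint, analysis, error rate or sample size changes. This is an inconsistency in how the tested intervention is specified, worth correcting because it is cheap to remove and bears on exposure, tablet counts and placebo matching.

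**What to change.** Reconcile the dosage-form column, the footnote and the dose column in Section 6.0 with one another, and with the strengths and source of drug in Section 4.0 (and the purchase statement in Section 5.0). The strength dispensed and the units per day should agree with the stated total daily dose at each step, for active drug and placebo alike, in Part I and in the extension. If the units are to be pharmacy-prepared, say so. Then check that the patient instructions in Appendix EEE and the accountability form in Appendix K use the same units per step, so that expected counts can be calculated.

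The dose and the formulation are for the clinical team; none is proposed here. The cost is protocol wording, plus the instruction sheet and form if the check shows that they differ. No extra patients or procedures are needed.
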